## **10. ADVERSE EVENT MANAGEMENT**

Patients should be instructed to notify their study team at the first occurrence of any adverse symptom. In addition to dose delays according to protocol guidance, investigators are encouraged to employ best supportive care according to local institutional clinical practice.

Recognizing that new knowledge will be acquired and unforeseen safety issues may arise in the course of the study, the management guidelines are not exhaustive and do not represent the full spectrum of care or treatment options described. The dose modification guidelines are not intended to replace clinical judgment or dictate care of individual patients.

In general, an adverse event related to study treatment that results in a dose delay should be present on the day of intended study treatment (i.e. a delayed toxicity that develops mid-cycle, but which is no longer present or has resolved to an acceptable grade on the day of intended dosing, generally does not require a delay in treatment – unless, for example, the occasion involves retrospective detection of a prior event of sufficient grade to, regardless of duration, require delay or discontinuation).

To prevent the development of more severe adverse events, treatment-related diarrhea, nausea and vomiting or rash should be managed early and proactively.

In the event of multiple toxicities, treatment delay should be based on the worst toxicity observed.

Even if study drug dosing is interrupted, tumor scans and other visits, assessments and procedures should continue per protocol (i.e. per timeline in place prior to the dose interruption).

Dose reductions for management of adverse event(s) within a given patient should be considered permanent: Once the dose of CB-839, panitumumab or irinotecan has been reduced in a given patient, all subsequent cycles in the same patient should be ordinarily administered at that dose level (unless additional dose reduction is required). Dose re-escalation may be discussed on a case-by-case basis with the Sponsor.

Thus, intrapatient dose re-escalation in a given patient will not ordinarily be allowed, unless there is discussion and agreement between the investigator and the sponsor-investigator (e.g. as part of an appropriate evaluation of the combinatorial setting in which, after strategic dose reduction of one or more particular agent, any potentially overlapping toxicity between CB-839, panitumumab and irinotecan is ultimately judged best attributed to one individual drug, but unlikely or not related to the other drugs).

#### **10.1. Definition of Dose-Limiting Toxicity**

When classified by the investigator as possibly, probably or definitely related to CB-839, or to the combination of CB-839 + panitumumab/irinotecan, any of the following events occurring during Cycle 1 (i.e. the first 28 days after first dose of CB-839) will be considered a dose-limiting toxicity:

##### **1) Non-Hematologic DLT:**

- Any  $\geq$  Grade 4 non-hematological toxicity
- Grade  $\geq$  3 total bilirubin or hepatic transaminases (ALT [SGPT] or AST [SGOT]) with the following exceptions:
  - Grade 3 elevated ALT/AST lasting for  $\leq$ 7 days and not associated with a more than 35% increase in abnormal direct bilirubin (i.e. bili is both  $>$ ULN and elevated  $>$ 35% over baseline) will not be considered a DLT
  - For patients with a Grade 1 hepatic transaminase level at baseline (i.e. ALT or AST), the same respective hepatic transaminase level must increase to  $>$ 7.5  $\times$  ULN to be considered a DLT.

- For patients with a Grade 2 hepatic transaminase level at baseline (i.e. ALT or AST), the same respective hepatic transaminase level must increase to  $> 10 \times \text{ULN}$  to be considered a DLT.
- Grade 3 other non-hematologic toxicity lasting  $> 3$  days despite optimal supportive care with the exception of:
  - Grade 3 fatigue
  - Grade 3 symptomatic rash that resolves to  $\leq$  Grade 1 within 3 weeks; or a Grade 3 asymptomatic rash
  - Grade 3 tumor flare (defined as local pain, irritation or rash localized at sites of known or suspected tumor)
  - A transient (resolves within 6 hours of onset) Grade 3 infusion-related AE
  - Grade 3/4 elevations in serum amylase and/or lipase lasting  $< 3$  weeks that are not associated with clinical or radiological evidence of pancreatitis.
- Any clinically meaningful (per investigator judgment) Grade 3 non-hematologic laboratory value if:
  - Medical intervention (other than electrolyte repletion) is required to treat the patient, OR
  - The abnormality leads to hospitalization, OR
  - The abnormality persists for  $> 1$  week.

2) **Hematologic DLT:**

- Grade  $\geq 3$  febrile neutropenia [ $\text{ANC} < 1.0 \times 10^9/\text{L}$  with either a single temperature of  $> 38.3^\circ\text{C}$  ( $101^\circ\text{F}$ ), or a sustained temperature of  $\geq 38^\circ\text{C}$  ( $100.4^\circ\text{F}$ ) for more than 1 hour]
- Grade 4 neutropenia ( $\text{ANC} < 0.5 \times 10^9/\text{L}$ ) lasting  $> 5$  days
- Grade 4 anemia lasting  $> 5$  days despite optimum management by transfusions
- Grade 4 thrombocytopenia ( $< 25.0 \times 10^9/\text{L}$ ) lasting  $\geq 7$  days
- Grade 4 thrombocytopenia ( $< 25.0 \times 10^9/\text{L}$ ) lasting  $< 7$  days if associated with:
  - A bleeding event that requires an elective platelet transfusion, OR
  - A life-threatening bleeding event which results in urgent intervention and admission to an Intensive Care Unit
- Any Grade 5 hematologic or non-hematologic toxicity excluding death due to disease progression

3) **DLT for inability to initiate Cycle 2 within 4 weeks of scheduled treatment**

- Due to slow recovery from adverse event classified by the investigator as possibly, probably or definitely related to CB-839, or to the combination of CB-839 + panitumumab/irinotecan and failure to meet protocol-defined retreatment criteria.

Subjects who have experienced a DLT do not automatically require discontinuation of protocol-indicated treatment, unless the nature or severity of the DLT is also an adverse event that would require permanent discontinuation of study as elsewhere defined by the protocol. Rather, a patient who has experienced a DLT should be evaluated for consideration of an appropriate dose hold or dose modification which, if consistent with the protocol, would allow continued dosing under revised circumstance.

Dose reductions are not allowed during the DLT window for a patient to count in dose-escalation decisions. After Cycle 1, dose reductions or interruptions for adverse events may take place at any time as otherwise consistent with the protocol.

For purpose of ensuring appropriate opportunity to determine the maximum tolerated dose (MTD) of CB-839 in combination with panitumumab + irinotecan, a subject who is withdrawn from the study prior to

completing the DLT assessment window (i.e. first 28 days after initiating protocol-indicated therapy on Cycle 1, Day 1) for reasons other than a DLT will not be considered evaluable for DLT and will be replaced.

Additionally, if a patient discontinues study treatment for reasons clearly not related to study treatment (in the judgement of the investigator), after completing less than 75% of scheduled oral doses of CB-839 and/or less than 2 planned infusions of panitumumab and 2 planned infusions of irinotecan over the first 28 days after initiating protocol-indicated treatment on Cycle 1, Day 1, then that patient will be considered not evaluable for response to overall protocol-indicated treatment and may be replaced with a new patient.

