**TABLE 7: Recommended Dose Modifications for Irinotecana**

Toxicity NCI CTC Grade b (Value)	Recommended Dose Modifications for Irinotecan
Neutropenia  1 (1500 to 1999/mm  ) 2 (1000 to 1499/mm  ) 3 (500 to 999/mm  ) 4 (< 500/mm  )	Maintain dose level Maintain dose level Omit dose until resolved to ≤ Grade 2, then ↓ 1 dose level Omit dose until resolved to ≤ Grade 2, then ↓ 2 dose levels
Febrile Neutropenia  ANC < 1000 /mm  with a single temperature of > 38.3 °C (101 °F) or a sustained temperature of ≥ 38 °C (100.4 °F) for more than one hour	Omit dose until resolved, then ↓ 2 dose levels
Other hematologic toxicities	Dose modifications for leukopenia or thrombocytopenia during a cycle of therapy and at the start of subsequent cycles of therapy are also based on NCI toxicity criteria and are the same as recommended for neutropenia above.
Diarrhea  1 (2-3 stools/day > pretx c ) 2 (4-6 stools/day > pretx) 3 (7-9 stools/day > pretx) 4 (≥10 stools/day > pretx)	Delay dose until resolved to Baseline c , then give same dose Omit dose until resolved to Baseline, then ↓ 1 dose level Omit dose until resolved to Baseline, then ↓ 1 dose level Omit dose until resolved to Baseline, then ↓ 2 dose levels
Other non-hematologic toxicitiesd  1 2 e 3 4	Maintain dose level Omit dose until resolved to ≤ Grade 1, then ↓ 1 dose level Omit dose until resolved to ≤ Grade 2, then ↓ 1 dose level Omit dose until resolved to ≤ Grade 2, then ↓ 2 dose levels

a Due to adverse events deemed (by patient's study physician) to be possibly, probably, or definitely related to irinotecan. Note: Patient's study physician may elect a more conservative course of irinotecan management.

b NCI Common Terminology Criteria for Adverse Events (CTCAE, version 4.03).

c Pretreatment and Baseline defined as the most immediately known status prior to initiating protocol-indicated irinotecan on Cycle 1, Day 1.

d Unless otherwise elected by the investigator: Excludes alopecia, anorexia, asthenia, fatigue; as well as nausea or vomiting that are not controlled with optimal management.

e Except alopecia, alkaline phosphatase elevation, asymptomatic lipase elevation

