## **12. SAFETY REPORTING OF ADVERSE EVENTS**

### **12.1. General**

Safety assessments will consist of monitoring and appropriate reporting AEs and SAEs that are considered possibly, probably or definitely related to the **investigational treatment (i.e. to CB-839, or to the combination of CB-839 + panitumumab/irinotecan) and research F-FSPG PET/CT scans**, all events of death, and any study-specific issue of concern.

Adverse event collection and reporting is a routine part of every clinical trial. Each adverse event will be graded according to the NCI's Common Terminology Criteria for Adverse Events (NCI CTCAE), Version 4.03, dated June 14, 2010, currently locatable via the following URL:

[http://evs.nci.nih.gov/ftp1/CTCAE/CTCAE\\_4.03\\_2010-06-14\\_QuickReference\\_8.5x11.pdf](http://evs.nci.nih.gov/ftp1/CTCAE/CTCAE_4.03_2010-06-14_QuickReference_8.5x11.pdf)

For events not listed in the CTCAE, severity will be designated as mild, moderate, severe or life threatening, or fatal which respectively correspond to Grades 1, 2, 3, 4, and 5 on the NCI CTCAE, with the following definitions:

- **Mild:** An event not resulting in disability or incapacity and which resolves without intervention;
- **Moderate:** An event not resulting in disability or incapacity but which requires intervention;
- **Severe:** An event resulting in temporary disability or incapacity and which requires intervention;
- **Life-threatening:** An event in which the patient was at risk of death at the time of the event;
- **Fatal:** An event that results in the death of the patient.

Information on all adverse events, whether serious or not, whether reported by the participant, directly observed, or detected by physical examination, laboratory test or other means, will be collected, recorded, followed and reported as described in the following sections.

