### **12.3. Risks Associated with Panitumumab and Irinotecan**

- The most common adverse reactions ( $\geq 20\%$ ) of panitumumab as monotherapy are: skin rash with variable presentations, paronychia, fatigue, nausea, and diarrhea.
- The most common adverse reactions ( $\geq 20\%$ ) in clinical trials of panitumumab in combination with FOLFOX chemotherapy are: diarrhea, stomatitis, mucosal inflammation, asthenia, paronychia, anorexia, hypomagnesemia, hypokalemia, rash, acneiform dermatitis, pruritus, and dry skin.
- Common adverse reactions ( $\geq 30\%$ ) observed in single agent therapy clinical studies of irinotecan are: nausea, vomiting, abdominal pain, diarrhea, constipation, anorexia, neutropenia, leukopenia (including lymphocytopenia), anemia, asthenia, fever, body weight decreasing, alopecia.
- Common adverse reactions ( $\geq 30\%$ ) observed in combination therapy clinical studies of irinotecan are: nausea, vomiting, abdominal pain, diarrhea, constipation, anorexia, mucositis, neutropenia, leukopenia (including lymphocytopenia), anemia, thrombocytopenia, asthenia, pain, fever, infection, abnormal bilirubin, alopecia.
- A more detailed safety profile of panitumumab and irinotecan are provided in the respective product labels, currently locatable online via following:

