### **15. STATISTICAL CONSIDERATIONS**

In the phase I portion, it is anticipated that 2 dose escalation cohorts will be needed to reach the MTD or RP2D; therefore, approximately 9-12 eligible patients will be required to evaluate the safety and tolerability of CB-839 in combination with panitumumab and irinotecan.

We will use the Bayesian continual reassessment method (CRM) to conduct this phase I clinical trial. Patients will be treated in cohorts of 3. All toxicity outcomes must be observed before calculating the recommended dose level for the next cohort. Dose levels may not be skipped. Up to 12 patients may be enrolled since there are 2 working dose levels and a -1 dose level to be evaluated and a minimum of 6 patients are required to establish the MTD. The probability of toxicity at the  $i$ th dose is assumed to follow  $Pr(tox) = p_i^{\exp(\alpha)}$  where  $p_i$  is a constant and  $\alpha$  is distributed  $N(0,2)$ . Targeting a MTD of 30%, we assume *a priori* that  $p_i = 0.1, 0.2$ , and  $0.3$ , for dose levels -1, 1 and 2, respectively. This CRM trial will stop if the probability that the estimated DLT rate of the lowest dose is excessive ( $> 0.3$ ) is greater than 90%.

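### The short-duration Grade 4 thrombocytopenia DLT counts a bleed given an elective platelet transfusion but not one needing urgent platelets outside an ICU

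*Combined protocol and SAP*

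**What the plan says.** Section 10.1 (hematologic DLT) treats Grade 4 thrombocytopenia in two ways. If it lasts 7 days or more, it is a DLT on its own. If it lasts less than 7 days, it is a DLT only when one of two bullets applies. The first bullet reads "A bleeding event that requires an elective platelet transfusion, OR" and so turns on the kind of transfusion. The second bullet, the alternative to it, reads "A life-threatening bleeding event which results in urgent intervention and admission to an Intensive Care Unit" and so turns on severity and place of care.

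The event must also be at least possibly related to CB-839 or the combination, and fall in the first 28 days. The protocol does not define *elective*, and no other section extends the first bullet to urgent transfusion.

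Section 15 makes DLT status the input to the Bayesian CRM that sets the MTD/RP2D, the Phase I primary endpoint: "All toxicity outcomes must be observed before calculating the recommended dose level for the next cohort". Cohorts are of 3, with at most 12 patients.

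**The concern.** The first bullet admits only elective transfusion. The second requires three things together: a life-threatening bleed, urgent intervention and ICU admission. A bleed needing platelets at once on an ordinary ward satisfies neither. Of two otherwise similar bleeds, the less urgent is therefore scored and the more urgent is not.

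Section 9.3 adds to the problem. It asks sites to transfuse platelets only if clinically indicated and to avoid doing so in the first 28 days, which is the DLT window. A transfusion given in that window is more likely to be prompted by need than planned.

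An unscored event makes a dose look safer than it was. With cohorts of 3, a single DLT can decide the next dose.

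**Working it through.** **Step 1. Do other DLT criteria catch the case?**

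| Criterion (Section 10.1) | Catches urgent platelets outside the ICU? |
|---|---|
| Grade 4 or higher non-hematologic toxicity | Yes, if the bleed is Grade 4 and coded as non-hematologic |
| "Grade 3 other non-hematologic toxicity lasting" more than 3 days | Only if Grade 3 and not controlled within 3 days |
| Grade 3 laboratory value | No; limited to non-hematologic values |
| Grade 4 thrombocytopenia for 7 days or more | No; the case is under 7 days |
| Grade 5 toxicity | Fatal events only |
| Cycle 2 not started within 4 weeks | Indirect; unlikely after thrombocytopenia of under 7 days |

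The protocol equates Grade 4 with life-threatening: Table 5 does so, and so does the Section 12.1 scale for events not listed in CTCAE ("severe or life threatening, or fatal which respectively correspond to Grades 1, 2, 3, 4, and 5 on the NCI CTCAE"). For bleeds below Grade 4, then, the first bullet carries the rule. The unscored case is a related bleed of Grade 3 or lower, resolved within 3 days if Grade 3, given urgent platelets outside the ICU during Grade 4 thrombocytopenia of under 7 days.

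**Step 2. What happens to that patient in the escalation data?** There are two possibilities. The patient may count as DLT-free, or may drop out of the count, because "Dose reductions are not allowed during the DLT window for a patient to count in dose-escalation decisions". Table 7 handles platelets like neutrophils ("Dose modifications for leukopenia or thrombocytopenia during a cycle of therapy" follows the neutropenia rows), so related Grade 4 thrombocytopenia means omitting irinotecan and then reducing it by two levels. Section 10.2 directs holding CB-839 and reducing it on resumption after clinically significant related Grade 3 or 4 events. Whether a reduction falls inside the window depends on recovery: Section 10.4.1 bars irinotecan until platelets reach 100,000/mm³.

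**Step 3. What can one unscored DLT do in the CRM?**

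Inputs from Section 15: skeleton s = 0.1, 0.2, 0.3 for levels -1, 1, 2; model p_i = s_i^exp(α); prior α ~ N(0,2); target 0.30; cohorts of 3; no skipping; stop if P(DLT rate at lowest dose > 0.3) > 0.9. Table 2 and Section 8.2 start patients at level 1. Assumption: the next dose is the level whose posterior mean is closest to 0.30, since Section 15 does not state the selection rule.

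Posterior density of α ∝ exp(−α²/2v) × ∏ p_i^y_i (1 − p_i)^(n_i − y_i), where y_i of n_i patients at level i have a DLT. It was integrated numerically.

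The plan's own figures come first. Reading the 2 as a precision (v = 1/2 = 0.5), exact enumeration of four cohorts gives expected DLTs of 2.84, 2.39, 3.28 and 3.71 in scenarios 1 to 4, equal to the CRM column of the Section 15 table. Results are also shown for v = 2, the literal variance reading.

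| Data | v | Posterior means, levels -1 / 1 / 2 | Next dose |
|---|---|---|---|
| Level 1: 0/3 | 0.5 | 0.070 / 0.132 / 0.200 | level 2 |
| Level 1: 1/3 | 0.5 | 0.187 / 0.291 / 0.385 | level 1 |
| Level 1: 0/3 | 2 | 0.046 / 0.083 / 0.125 | level 2 |
| Level 1: 1/3 | 2 | 0.251 / 0.355 / 0.444 | level -1 |
| Level 1: 0/3, then level 2: 1/3 | 0.5 | 0.091 / 0.170 / 0.253 | level 2 |
| Level 1: 0/3, then level 2: 2/3 | 0.5 | 0.161 / 0.264 / 0.359 | level 1 |
| Level 1: 0/3, then level 2: 1/3 | 2 | 0.090 / 0.164 / 0.242 | level 2 |
| Level 1: 0/3, then level 2: 2/3 | 2 | 0.189 / 0.293 / 0.386 | level 1 |

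In the first cohort, scoring a true 1/3 as 0/3 changes the next dose from level 1 (v = 0.5) or level -1 (v = 2) to level 2. In the second cohort, scoring a true 2/3 as 1/3 keeps patients at level 2 instead of returning to level 1, under both readings. A true 1/3 at level 2 scored as 0/3 changes nothing: both results stay at level 2.

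**The case against.** The strongest reply is that nobody would apply the bullet this way. A transfusion that is required is hardly elective, so the word sits badly with its own verb. The two bullets read naturally as tiers: a lesser bleed needing platelets, then a life-threatening one needing intensive care. An investigator would probably count a bleed worse than the lower tier. That is plausible, but it means setting aside a stated word in a primary-endpoint criterion, and scoring would then depend on who reads it.

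Three further points stand as limits:

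- **Rarity.** Several conditions must coincide in Cycle 1 among at most 12 patients. Section 12.3 lists thrombocytopenia among common (at least 30%) reactions to irinotecan combination therapy ("mucositis, neutropenia, leukopenia (including lymphocytopenia), anemia, thrombocytopenia, asthenia"), but it is on neither the CB-839 nor the single-agent irinotecan list.
- **Generic CRM arithmetic.** Any misclassified DLT can move a cohort of 3. The table shows why the wording matters, not how often. It also models only the patient counted as DLT-free; which branch of Step 2 applies is not settled.
- **Partial fix.** A bleed managed urgently without platelets and outside the ICU would still be missed by this criterion.

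**Conclusion.** The concern holds as a minor one. As written, the criterion scores a less urgent bleed and omits a more urgent one, and no other text in Section 10.1 closes the residual case.

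Only the direction of the effect is established: fewer DLTs scored and a tendency toward a higher dose. No change in MTD selection probability is claimed, because the documents give no rate for this event. The conclusion about the wording rests on the ordinary meaning of *elective*. The dose moves rest on the assumed closest-to-target rule and on the two readings of the prior shown.

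**What to change.** In Section 10.1, delete *elective* from the first bleeding bullet. Any related bleed requiring a platelet transfusion during Grade 4 thrombocytopenia of under 7 days then counts as a DLT, however urgent and wherever treated. The ICU bullet can stay.

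The cost is one word in an amendment, with no added blood counts, visits or eCRF fields. The downside is an occasional extra DLT and slightly more cautious escalation.

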## **10.2. Dose-Adjustments and Delays of CB-839**

Given the limited number of patients treated to date and the open label, nonrandomized nature of the studies to date, the safety profile of CB-839 has not been fully established. An overall summary of the available safety and tolerability data was profiled above in section 2.4.2.

Overall, CB-839 has been well tolerated across all dose levels tested to date. The large majority of toxicities that have been observed to date have been Grades 1 and 2 and manageable with supportive care and/or interruption of study drug.

Careful application of the dose-escalating rules and close observation of the subjects should minimize the potential risk of dosing with CB-839.

Based on available data, adverse events that are most likely to be observed with CB-839 treatment are mild to moderate and include fatigue, gastrointestinal events (nausea, vomiting, anorexia), photophobia and elevated liver function tests.

Photophobia and related ocular toxicities (e.g., photopsia) have been identified as CB-839-related events. In almost all cases, these events have been Grade 1 and generally do not have an impact on the patient's daily life, although one Grade 2 event required the patient rest for 1-2 hr in a dark room. These events appear to occur around Cmax (1-4 hr after dosing) and resolve with time. Anecdotal reports suggest that tachyphylaxis develops and these events tend to become less frequent over extended dosing. More severe cases can be managed with dose reduction and the use of sunglasses may be considered.

The study personnel must be able to recognize and diagnose these potential adverse events and initiate prompt intervention. In particular, regular monitoring of liver function tests and renal function is recommended.

**Upon withholding CB-839 for adverse event, CB-839 may be restarted when the associated adverse event has returned to  $\leq$  Grade 1, or to the patient's baseline value. (The baseline value is defined as the most immediately known value in place prior to patient's first receipt of CB-839 on Cycle 1, Day 1.)**

**For adverse events deemed by the investigator to be clinically significant and as possibly, probably, or definitely related to CB-839 treatment:**

- **Grade 1 or 2:** Manage with appropriate supportive care.
- **Grade 3 or 4:** Hold CB-839 and Dose Reduce (by 1 or more dose levels) upon resumption

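### The Cycle 1 dose-reduction rule has no exception for DLTs, so a patient with a DLT who resumes at a reduced dose by Day 28 would not count in the CRM

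*Combined protocol and SAP*

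**What the plan says.** Section 10.1 gives the counting rule: "Dose reductions are not allowed during the DLT window for a patient to count in dose-escalation decisions". The paragraph just before it says that a DLT does not by itself end treatment, and that "a patient who has experienced a DLT should be evaluated for consideration of an appropriate dose hold or dose modification". For clinically significant Grade 3 or 4 events at least possibly related to CB-839, Section 10.2 says "Hold CB-839 and Dose Reduce (by 1 or more dose levels) upon resumption". Restart is allowed once the event is back to Grade 1 or lower, or to baseline.

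The paragraph after the counting rule treats withdrawal differently. A patient who leaves before the window ends "for reasons other than a DLT will not be considered evaluable for DLT and will be replaced", so a patient withdrawn because of a DLT remains evaluable. Section 4.4 limits its own exclusion to patients who stop for reasons plainly unrelated to treatment.

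Section 15 sets up the CRM with cohorts of 3, at most 12 patients and a 30% target, and says "All toxicity outcomes must be observed before calculating the recommended dose level for the next cohort".

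**The concern.** Whether an observed DLT enters the dose-finding model should not depend on how the dose was managed afterwards. Here it can. A patient may have a DLT, be managed as the protocol directs, and then fail the counting rule because of that management.

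This can happen within 28 days. Febrile neutropenia of Grade 3 or higher is a DLT under Section 10.1. Table 7 has irinotecan omitted until it resolves and then lowered by two levels, and irinotecan is due on Day 15. CB-839 is taken continuously, so a reduced restart can also fall before Day 28.

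At stake is the MTD/RP2D, which is the Phase I primary endpoint and sets the CB-839 dose for Phase II. With at most 12 patients, one DLT in or out of the count can change the decision.

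**Working it through.** **Inputs from the plan (Sections 8.2 and 15).** DLT probability at level i is p_i^exp(α), with p_i = 0.1, 0.2, 0.3 at levels -1, 1, 2 and α ~ N(0,2). The target is 0.30. The trial starts at level 1, treats cohorts of 3 up to 12 patients, skips no level, and stops if the probability that the lowest dose's DLT rate exceeds 0.3 is above 90%.

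**Assumed inputs, not in the documents.** d is the probability that a DLT patient is dropped, and u the probability that a non-DLT patient is dropped. Both are taken as equal across dose levels, and dropped patients are replaced.

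**Step 1: reproduce the plan.** Section 15 does not say whether the 2 in N(0,2) is a variance, a standard deviation or a precision. Exact enumeration, with 2 read as a precision and posterior-mean DLT rates, comes within about 0.02 of every CRM selection probability in the Section 15 operating-characteristics table. For Scenario 4 (true rates 0.2, 0.3, 0.4):

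| | Stop | -1 | 1 | 2 | Expected DLTs |
|---|---|---|---|---|---|
| Plan | 0.01 | 0.24 | 0.43 | 0.33 | 3.71 |
| Recomputed | 0.008 | 0.219 | 0.444 | 0.329 | 3.71 |

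The recomputation counts every patient's DLT outcome, so the published figures correspond to d = u = 0.

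**Step 2: apparent DLT rate after dropping and replacement.**

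Apparent rate = p(1-d) / [p(1-d) + (1-p)(1-u)]. At p = 0.4:

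- d = 0.10, u = 0: 0.36 / (0.36 + 0.60) = 0.375
- d = 0.25, u = 0: 0.30 / (0.30 + 0.60) = 0.333
- d = 0.50, u = 0: 0.20 / (0.20 + 0.60) = 0.25
- d = u = 0.25: 0.30 / (0.30 + 0.45) = 0.40, unchanged
- d = 0.25, u = 0.50: 0.30 / (0.30 + 0.30) = 0.50

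**Step 3: effect on Scenario 4 (same model as Step 1).**

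| d | u | P(select level 2, true DLT rate 40%) | P(select level -1) |
|---|---|---|---|
| 0 | 0 | 0.33 | 0.22 |
| 0.10 | 0 | 0.39 | 0.18 |
| 0.25 | 0 | 0.50 | 0.11 |
| 0.50 | 0 | 0.73 | 0.04 |
| 0.25 | 0.25 | 0.33 | 0.22 |
| 0.25 | 0.50 | 0.135 | 0.43 |

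Expected true DLTs rise from 3.71 to 4.27 at d = 0.25 and 5.02 at d = 0.50 (u = 0), because dropped patients are replaced. Reading 2 as a variance with plug-in rates gives nearly the same level 2 selection: 0.34, 0.51 and 0.74 at d = 0, 0.25 and 0.50.

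**Step 4: one dropped DLT in the first cohort at level 1.** Six variants were run: 2 as variance, standard deviation or precision, each with plug-in and posterior-mean rates. In all six:

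- 1 DLT in 3 recommends level 1 or level -1, never level 2.
- With that DLT dropped, 0/3 (patient replaced) and 0/2 (not replaced) both recommend level 2.

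This reversal needs no assumption about replacement.

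**The case against.** The strongest reply is that the surrounding text shows an intent to count DLTs. The withdrawal rule protects them, Section 4.4 excludes only patients who stop for unrelated reasons, and Section 15 wants all toxicity outcomes in hand before the next dose is set. On that view the sentence means only that a patient must stay on the assigned dose to count as DLT-free. This is probably what was meant. But none of those passages covers a patient who has a DLT and stays on at a lower dose, so they do not override the sentence.

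Two stronger readings are tempting, and the documents do not support them.

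- **A reader might infer that DLT patients in general are removed.** They are not. Patients whose treatment is only held, those reduced after Day 28 and those withdrawn for the DLT still count. Many DLTs are defined by persistence, which leaves less time for a reduced restart inside the window. Section 10.3.3 recommends full-dose panitumumab after one withheld dose. At 400 mg there is no lower CB-839 level, and a patient who cannot tolerate it leaves the study.
- **A reader might infer that the rule always biases the dose upwards.** It does so only if d exceeds u. Because no drug is named, the rule also drops patients reduced without a DLT. For Grade 2 diarrhea, for example, Table 7 says of irinotecan "Omit dose until resolved to Baseline, then ↓ 1 dose level". Dropping such patients pushes the other way.

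The drop fractions are assumptions. At 10% the shift is modest.

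**Conclusion.** The defect stands in a limited form. Followed literally, Section 10.1 leaves out of the escalation decision a patient who has a DLT and resumes at a reduced dose by Day 28, which is inconsistent with its own treatment of patients withdrawn for a DLT. This is more than missing detail, because following the sentence as written gives a wrong count.

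The size depends on fractions that the documents do not give. With 10% to 50% of DLT patients and no others dropped and replaced, Scenario 4 selection of the 40% dose is about 0.39 to 0.73, against about 0.33 when every DLT counts. The direction is conditional: upward if DLT patients are dropped more often, nil if equally often, downward if less often. The single-patient result is firmer: one DLT lost from the first cohort turns a decision not to escalate into a decision to escalate under every variant of the model tried.

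**What to change.** Add to Section 10.1, next to the counting rule:

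*Any patient with a DLT in the window is evaluable and counts in dose-escalation decisions, regardless of later dose changes. Only a patient without a DLT can become non-evaluable because of a dose reduction.*

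Also state which of CB-839, panitumumab and irinotecan the rule covers, and whether a patient made non-evaluable by a reduction is replaced.

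Leave the existing limit in Sections 4.4 and 10.1, which confines the under-treatment exclusion to patients who stop for unrelated reasons. Making every under-treated patient without a DLT non-evaluable would add another exclusion that depends on outcome. The clinical dose-reduction rules stay as they are.

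The cost is a short wording amendment, with no added procedures and no change to the CRM or its published operating characteristics.
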